8.7.9. Time from Initial to Repeat-Treatment

Time (in days) from initial treatment to repeat-treatment for subjects received Princess® FILLER Lidocaine and Juvéderm® Ultra XC. This endpoint will be analyzed using descriptive statistics.

8.7.10. Injection Volume for Optimal Correction

Injection volume (initial, touch-up and repeat-treatments, separate assessments) needed for optimal correction for subjects received Princess® FILLER Lidocaine and Juvéderm® Ultra XC. This endpoint will be analyzed using descriptive statistics.

This document is confidential.

9. Safety

The population used for safety analyses will be the SAF. Safety will be assessed on the basis of adverse events (AEs), adverse device effects (ADEs) reports, serious adverse events (SAEs) and serious adverse device effects (SADEs).

9.1. Extent of Exposure

Injection volume (mL) administered and number of syringes used will be summarized for the SAF using descriptive statistics (number of subjects, mean, SD, median, minimum, and maximum) by treatment type (initial, touch-up, repeat, and total). In addition, injection volume (mL) administered will be presented for overall treatment by treatment type (initial, touch-up, repeat, and total).

9.2. Treatment Compliance

N/A.

9.3. Adverse Events / Adverse Device Effects / Injection Site Responses

An Adverse Event (AE) is any untoward medical occurrence, unintended disease or injury or any untoward clinical signs in subjects, users or other persons administered a pharmaceutical product and which does not necessarily have to have a causal relationship with the treatment. An AE can therefore be any unfavorable and unintended sign (including an abnormal laboratory finding), symptom, or disease temporally associated with the use of a medicinal (investigational/experimental) product, whether or not related to this product. Treatment, Princess® FILLER Lidocaine or Juvederm® Ultra XC, was based on the AE side of face; if AE side is not applicable (N/A), the AE is considered to have happened to both sides of the face.

A Serious Adverse Event (SAE) is defined as an AE meeting one or more of the following conditions:

- Led to death;
- led to serious deterioration in health of the subject that either resulted in:
 - a life-threatening illness or injury, or
 - a permanent impairment of a body structure or a body function, or
 - in subject hospitalization or prolonged hospitalization, or
 - medical or surgical Intervention to prevent life-threatening illness or injury or permanent impairment to a body structure or a body function
- Led to fetal distress, fetal death, or a congenital abnormality or birth defect;
- Is an important medical event.

An Adverse Device Effect (ADE) is an adverse event related to the investigational medical device. This includes any AE resulting from insufficiencies or inadequacies in the instructions for use, the deployment, the implantation, the installation, the operation, or any malfunction of the investigational medical devices. In addition, this includes any event that is a result of a use error or intentional misuse of the investigational medical devices.

A Serious Adverse Device Effect (SADE) is an ADE, in a participant, user or other person that results in any outcome listed in the definition of Serious Adverse Event. This includes device deficiencies that might have led to a Serious Adverse Event, in a participant, user, or other person if a) suitable action had not been taken or b) intervention had not been made or c) if circumstances had been less fortunate. These are handled under the SAE reporting system.

- If the start date is completely missing, an AE will be considered treatment-emergent unless the stop date is before study product administration.

Device-related TEAEs/ TEADEs are defined as TEAEs/ TEADEs with possible or probable or definite relationship to study device.

Treatment-emergent AEs and ADEs will be summarized using the latest version of Medical Dictionary for Regulatory Activities (MedDRA) by System Organ Class (SOC) and Preferred Term (PT), classified from verbatim terms. The incidence and percentage of participants with at least 1 occurrence of a PT will be included, according to the most severe grade using a 3-point scale (mild, moderate, severe). The number of events per PT will also be summarized. Causality (relationship to study treatment) will be summarized separately.

The number and percentage of subjects as well as number of events will be presented for the treatment-emergent AEs and ADEs summaries. For summaries by SOC and PT, a subject will be counted once at the SOC level and once at each PT within the SOC level. For summaries by SOC, PT, and maximum severity, a subject is counted once at the highest severity level for which the event occurred at the SOC level and the highest severity level for each unique PT within that SOC level. Therefore, subjects may only contribute once to each PT and once to each SOC level.

Only injection site reaction AEs will be summarized by treatment group. However all AEs will be summarized by overall for both treatment groups together.

This document is confidential.

The incidence and frequency of treatment-emergent AEs, ADEs, SAEs, SADEs, and special interest AEs will be summarized by treatment group for injection site reaction AEs, and all AEs will be summarized by overall according to SOC and PT. AEs and ADEs will also be listed. The duration of AEs and ADEs will be determined and included in listings, along with the action taken and outcome.

Summaries presenting frequency of treatment-emergent AEs/ ADEs by SOC and PT will be ordered by overall descending frequency of SOC and then, within a SOC, by overall descending frequency of PT.

AEs, ADEs, SAEs and SADEs will be listed by subject and treatment group for injection site reaction AEs, and overall for non injection site reaction AEs and then chronologically by date and time of onset. These listings will include all data collected in the eCRF, along with the derived variables: elapsed time since initial application, duration, and coded variables.

The following summaries will be provided:

- An overall summary of the number and percentage of treatment-emergent AEs and ADEs, serious TEAEs and TEADEs, severity TEAEs and TEADEs (unanticipated and anticipated), device-related TEAEs and TEADEs, procedure-related TEAEs and TEADEs, sepecial interest TEAEs, TEAEs and TEADEs leading to study withdrawal, and death;
- Treatment-emergent AEs and ADEs by SOC and PT;
- Treatment-emergent AEs and ADEs by SOC, PT and maximum severity;
- Treatment-emergent AEs and ADEs by SOC, PT and maximum relationship to study device/procedure;
- Treatment-emergent serious AEs and ADEs by SOC and PT;
- Study device/procedure related Treatment-emergent AEs and ADEs by SOC and PT;
- Special Interest Treatment-emergent AEs by SOC and PT;
- Treatment-emergent serious AEs and ADEs by SOC, PT and maximum relationship to study device/procedure;
- List of treatment-emergent AEs and ADEs Leading to study withdrawal.

TEAEs and TEADEs of the repeat-treatment subgroup from Week 36 or Week 48 or Visit 7c will be separately summarized.

Deaths, other serious and significant adverse events (if any) will be listed separately.

The number and percentage of subjects with injection site reactions by maximum severity, and duration of injection site reactions will be summarized by treatment group.

Injection site reactions will be listed. In addition, injection site reactions not resolved after 14 days (after initial treatment, touch-up treatment, repeat treatment), will be classified as an AE per investigator discretion, and all these AEs will be listed.

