The primary effectiveness outcome measure will be evaluated by means of a one-sided 95% confidence interval for the difference in paired proportions p_A - p_B . At this, p_A is the response rate for Princess® FILLER Lidocaine and p_B is the response rate for Juvéderm® Ultra XC. Thus, a negative value for this difference means that the response rate of Princess® FILLER Lidocaine is lower than the response rate for Juvéderm® Ultra XC. Princess® FILLER Lidocaine will be considered non-inferior to Juvéderm® Ultra XC if the lower confidence limit exceeds the non-inferiority margin of -10% and thus if the null hypothesis H_0 : p_A - $p_B \le -10\%$ can be rejected. In addition to this, the response rates for both treatment groups will be tabulated.

The statistical analysis of the secondary and additional outcome measures will be described in detail in the statistical analysis plan. A hierarchical testing procedure will be applied for the analysis of the primary outcome measure, as well as the secondary outcome measures 1 and 2, in order to control multiplicity. For qualitative variables, the frequencies (absolute and relative) will be calculated

and compared between the treatment groups. Quantitative parameters will be described by declaring the mean value, standard deviation, minimum, first quartile, median, third quartile, and maximum per treatment group. In addition to this, mean value, standard deviation, minimum, first quartile, median, third quartile, and maximum will also be provided for the difference in quantitative parameters between the two treatment sides of a subject. Secondary outcome measures 1 and 2 will be analyzed as described for the primary effectiveness outcome measure. Descriptive statistics will be used to summarize the remaining outcome measures. Adverse events will be summarized by treatment, preferred term and system organ class, and also by intensity, duration, causal relationship to the device or procedure, and seriousness.

Page 32 of 133

CPH-301-201200F

2.1

Schedule of Clinical Investigation Procedures and Assessments

					Folle	w-up for i	nitial -/touc	Follow-up for initial -/touch-up treatment	ent	Evaluation	for repeat-tr	eatment/rep	Evaluation for repeat-treatment/repeat-treatment	Follow-up for repeat-treatment	peat-treatment ⁵

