5.5 Safety Objectives

To assess frequency, severity, seriousness and causal relationship of AEs, ADEs, SAEs, and serious adverse device effects (SADEs) during the entire clinical investigation period including subjects complaints recorded in the subject diaries during the four weeks following initial-, touch-up- and repeat-treatments, as in comparison with Juvéderm® Ultra XC.

Risks and Benefits of the Investigational Device and Clinical Investigation

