2.4. Safety Objectives

To assess frequency, severity, seriousness and causal relationship of adverse events (AEs), adverse device effects (ADEs), serious adverse events (SAEs) and serious adverse device effects (SADEs) during the entire clinical investigation period including subject complaints recorded in the subject diaries during four weeks after initial- and touch-up-treatments, in comparison with Juvéderm® Ultra XC and during four weeks after repeat-treatments, for Princess® FILLER Lidocaine.

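### SAP 9.3 tabulates adverse events by filler only if they are classed as injection-site reactions; other one-sided events are tabulated only pooled, an undeclared narrowing of a comparative safety plan

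*SAP*

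**What the plan says.** **The reporting rule.** SAP 9.3: "Only injection site reaction AEs will be summarized by treatment group. However all AEs will be summarized by overall for both treatment groups together". The next sentence names treatment-emergent AEs, ADEs, SAEs and SADEs and continues: "special interest AEs will be summarized by treatment group for injection site reaction AEs, and all AEs will be summarized by overall". For listings, injection-site-reaction AEs are ordered by treatment group, and the rest are shown "overall for non injection site reaction AEs". Injection-site reactions are also summarised by treatment group for maximum severity and duration.

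**The attribution rule.** The same section assigns each AE to a filler by side of face and adds that "if AE side is not applicable (N/A), the AE is considered to have happened to both sides of the face".

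**The objective.** SAP 2.4 covers AEs, ADEs, SAEs and SADEs, including diary complaints "during four weeks after initial- and touch-up-treatments, in comparison with Juvéderm® Ultra XC"; after repeat-treatment it concerns Princess FILLER Lidocaine only. SAP 3.4 words the outcome measure the same way. Protocol 5.5 also ends "as in comparison with Juvéderm® Ultra XC".

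**The protocol's analysis.** Synopsis, Planned Statistical Analysis: "Adverse events will be summarized by treatment, preferred term and system organ class". It sets no limit to injection-site reactions.

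**Declared changes.** SAP section 11 lists the estimand approach and the use of confidence intervals or p-values for the lower-ranked objectives. It does not mention AE reporting.

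**The concern.** In a split-face design each subject carries both fillers, so an event confined to one side bears directly on one of them. Pooling is reasonable for a systemic event, because both fillers are in the same person. For a one-sided event it removes the comparison that the design makes possible.

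SAP 9.3 decides which table an event enters by its classification as an injection-site reaction, not by whether a side was recorded. Colour change around the eyelids is named in SAP 9.3 as an event of special interest and can occur on one side. If it is not classed as an injection-site reaction, no by-filler table is planned for it. The text does not define an injection-site-reaction AE, so which events are compared is left to a later coding decision. At stake is whether the report can set out, in a planned table, how such device effects divide between the two products.

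**Working it through.** The documents give no sample size, event rate or power for safety, so there is no planned figure to reproduce. The check is of the texts against each other, followed by an illustration.

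**1. What each event type receives, for onset before repeat-treatment.** I read treatment group in SAP 9.3 as filler, because SAP section 8 uses it that way and the side rule in 9.3 assigns fillers.

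| Event | By-filler table | Pooled table | Side readable in listings |
|---|---|---|---|
| Classed as injection-site reaction, including any ADE, SADE or special-interest event so classed | yes | yes | yes |
| Left or right side recorded, not so classed | no | yes | yes |
| No side (N/A) | no, unless so classed | yes | not applicable |

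Only the second row is at issue. The listings column rests on the SAP 9.3 statement that listings carry all eCRF data, and on side being among those data, as the attribution rule presupposes.

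**2. Against the objective.** The objective and outcome measure name four event classes and a comparator, with no restriction to injection-site reactions. The second row falls within them and gets no comparative table.

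**3. Against the protocol's analysis.** The synopsis plans AEs by treatment, and the SAP limits this to one subset. Section 11 is where such a change belongs, and it is silent.

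**4. Against the attribution rule.** Injection-site events normally have a side. If only they are tabulated by filler, the N/A clause has little to act on, and the side rule goes unused for everything else.

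**5. What a pooled row cannot show.** Assumptions, none taken from the plan's safety text: 270 treated subjects (the planned number randomised); *k* events, each in a different subject and on one side only; *x* of them on the more affected filler.

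- Pooled row: *k*/270, whatever *x* is.
- Exact two-sided sign test, for illustration only: p = 2 × Σ C(*k*, *j*) / 2^*k*, summed over *j* = *x* to *k*.

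| Split | Pooled row | p |
|---|---|---|
| 6:0 | 6/270 = 2.2% | 2 × 1/64 = 0.031 |
| 8:0 | 8/270 = 3.0% | 2 × 1/256 = 0.008 |
| 9:1 | 10/270 = 3.7% | 2 × (10 + 1)/1024 = 0.021 |
| 10:2 | 12/270 = 4.4% | 2 × (66 + 12 + 1)/4096 = 0.039 |

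A 5:5 split gives the same pooled row as 9:1.

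**6. Why N/A events should stay out of the filler columns.** If *m* such subjects are counted on both sides, *x* against *y* becomes *x* + *m* against *y* + *m*. The difference is unchanged, but the ratio moves towards 1 and a one-sided pattern is harder to see.

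**The case against.** **Most device effects may already be compared.** Any ADE, SADE or special-interest event classed as an injection-site reaction is tabulated by filler. Protocol 4.1 and 4.4.3 report that, in an earlier post-market study of the filler without lidocaine, every ADE except two headaches was at the injection site. This stands, and it confines the point to the second row of the table above.

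**The information is not lost.** Serious events, special-interest events, serious ADEs and withdrawals each have their own listing, and side should be readable there. With a handful of events, a reader can count sides. This stands too: what is missing is the planned tabulation.

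**The objective can be read more narrowly.** In SAP 2.4 the comparison follows the diary clause and might govern only diary data, which are compared by filler. Protocol 14.2 plans AE incidence with no treatment split and mentions treatment only for the listing. The wording does leave room. But the sentence opens with all four event classes, and the synopsis is explicit, so the SAP should at least reconcile the texts.

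**Several candidate examples are weak.** The protocol presents numbness as a limb or stroke symptom and puts herpes reactivation among possibly unrelated events. Vascular occlusion has its own suspension and root-cause process. None is relied on here.

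**The shells are a separate document** and were not available. Some AE tables are indexed twice under one title, so their columns cannot be settled from the index. The rule in SAP 9.3 is nevertheless explicit.

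**Conclusion.** The point holds for one class of event: those with a recorded left or right side, onset before repeat-treatment, and no injection-site-reaction classification. For these, SAP 9.3 states a rule that drops a by-filler table which the protocol synopsis plans and the safety objective, on its natural reading, calls for. The change is not declared.

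A reader might infer that the plan compares no device effects, SADEs or special-interest events between fillers, or that it could never reveal a difference. The documents do not support either: events classed as injection-site reactions are compared, and the listings keep the side of the others.

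The size is unknown. It depends on how many such events occur and on where the undefined boundary is drawn. The illustration rests on assumed counts and on a test that the SAP does not plan, since its AE reporting is descriptive. It shows only that a pooled row is blind to the split. The primary effectiveness conclusion is not affected. The change is worth making because it is specific and cheap.

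**What to change.** 1. In SAP 9.3 and the TEAE, ADE, SAE, SADE and special-interest tables, add a column per filler for every event with a recorded left or right side and onset before repeat-treatment. After that visit both folds of a retreated subject receive Princess FILLER Lidocaine, so side no longer separates the products. Keep the pooled column.
2. Show N/A-side events in the overall column only. This contradicts the current rule that counts them on both sides, so amend that rule in the same section.
3. State which terms count as injection-site-reaction AEs. While doing so, reconcile when an unresolved reaction may become an AE: SAP 9.3 says after 14 days, and protocol 12.4 says when the diary is returned after 4 weeks.
4. If any restriction on by-filler reporting is kept, list it in SAP section 11 with the reason.

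The cost is a few extra columns, mostly with small counts, one changed derivation rule and one definition. No new data are needed, because side of face is already the SAP's basis for assigning an event to a filler. Small counts in the new columns should be read descriptively.

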9.4 Subject Enrollment, Number and Duration of Subject's Participation

Subjects who have signed the informed consent form (ICF) and comply with all inclusion and exclusion criteria will be enrolled, and undergo treatment at Visit 2 on Day 0. Screening and Baseline may be combined in one visit. If full correction is not achieved after the initial treatment, subjects may receive a touch up treatment 2 weeks later and can receive repeat-treatment (with Princess® Filler Lidocaine only) at Week 36 (Visit 6) or Week 48 (Visit 7) or Visit 7c. Each subject is expected to be in the clinical investigation for a maximum of 104 weeks including the temporary hold on repeat-treatment.

CPH-301-201200F

Approximately 300 subjects will be screened in the USA; the enrollment of a total of approximately 270 subjects is planned in order to obtain at least 240 evaluable subjects randomized in an 1:1 ratio to each clinical investigation group (accounting for a screening failure rate of approximately 10%, as well as approximately 10% of subjects to be excluded from the Per-Protocol Set due to major protocol deviations or subjects lost to follow-up).

The clinical investigation is planned to be conducted at approximately 10-12 US sites with enrolment target of 23-27 subjects per site. Competitive recruitment may be allowed to stimulate enrollment, but no site will be allowed to enroll more than 54 subjects (20%) unless prior approval of the sponsor is given; in this case, the maximum number of subjects per site is capped at 68 (25%). This will maintain adequate balance between the investigational sites.

10

Clinical investigation Procedures and Assessments

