10.11.13 Week 48 (Visit 9a), Week 60 (Visit 9b) or Visit 9c

The following assessments will be performed at the end of clinical investigation visit at Week 48 (\pm 5 days), Week 60 (\pm 5 days) or Visit 9c (\pm 5 days), which are twelve weeks after repeat-treatment:

- In case repeat-treatment was performed at Week 36 (Visit 6), Week 48 (Visit 7) or Visit 7c, visual examinations (including Snellen visual acuity, confrontational visual fields and ocular motility). For action to be taken in case of abnormal findings, see Section 10.8.4.
- Body weight measurement
- AEs
- Concomitant medications/procedures

For subjects who are not retreated at Week 36 (Visit 6) or Week 48 (Visit 7), the Week 48 Visit will be their end of study visit unless the subject returns for Visit 7c. For subjects who are not retreated at Visit 7c, Visit 7c will be their end of study visit. For subjects who are retreated at Week 36, the Week 48 Visit will be their end of study visit. For subjects who are retreated at Week 48, the Week 60 Visit will be their end of study visit. For subjects who are retreated at Visit 7c, Visit 9c (12 weeks after Visit 7c) will be their end of study visit.

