2.5. Brief Description

This is a randomized, subject- and evaluating investigator-blinded, controlled, multicenter, split-face comparison clinical investigation of Princess® FILLER Lidocaine compared to Juvéderm® Ultra XC in the treatment of moderate to severe NLFs.

Eligible subjects will be randomized at Baseline (Visit 2/Day 0) in a 1:1 ratio to Group A or Group B and will receive an injection of Princess® FILLER Lidocaine and an injection of Juvéderm® Ultra XC as follows:

Group A:

- Princess® FILLER Lidocaine on left NLF
- Juvéderm® Ultra XC on right NLF

Group B:

- Juvéderm® Ultra XC on left NLF
- Princess® FILLER Lidocaine on right NLF

The left NLF will be treated first and the right NLF thereafter.

The initial treatment will be administered at Baseline (Visit 2/Day 0) after randomization.

A touch-up treatment may be done at Visit 3a (Week 2) if an optimal aesthetic correction has not been achieved after initial treatment, as evaluated by the treating investigator. A touch-up treatment will be performed using the same type of device as initially applied.

A repeat-treatment may be done at Visit 6 (Week 36) or Visit 7 (Week 48) or Visit 7c (post repeat-treatment hold follow-up visit), if in the opinion of the treating investigator, the subject has returned to sufficient severity of NLFs that would have qualified them for enrollment into the clinical investigation initially. A repeat-treatment will be performed with Princess® FILLER Lidocaine on both NLFs.

Repeat-treatment:

Subjects who received repeat-treatment at Visit 6 (Week 36) or Visit 7 (Week 48) or Visit 7c (post repeat-treatment hold follow-up visit) will be included in the repeat-treatment subgroup, and the demographic, other baseline characteristics, medication, and applicable safety data will be analyzed by Group A, Group B, and repeat-treatment subgroup.

Subjects who received a repeat-treatment at Visit 6 (Week 36) will come back for safety follow-up visits at Visit 8a (Week 40) and at Visit 9a (Week 48). For these subjects, Visit 9a will be their end of study visit. Subjects who received a repeat-treatment at Visit 7 (Week 48) will come back for safety follow-up visits at Visit 8b (Week 52) and at Visit 9b (Week 60). For these subjects, Visit 9b will be their end of study

This document is confidential.

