Table 14.2.3.9.1	Additional Effectiveness Analysis Time from Initial to Repeat-Treatment in Days	FAS
Table 14.2.3.9.2	Additional Effectiveness Analysis Time from Initial to Repeat-Treatment in Days	PPS
Table 14.2.3.10.1	Additional Effectiveness Analysis Injection Volume Needed for Optimal Correction in Milliliter (mL)	FAS
Table 14.2.3.10.2	Additional Effectiveness Analysis Injection Volume Needed for Optimal Correction in Milliliter (mL)	PPS
Section 14.3 Safety Data		
Table 14.3.1.1.1.1	Overall Summary of Treatment-Emergent Adverse Events for Initial-treatment	SAF
Table 14.3.1.1.1.2	Overall Summary of Treatment-Emergent Adverse Events for Initial-treatment	SAF
Table 14.3.1.1.2	Overall Summary of Treatment-Emergent Adverse Events for Repeat-Treatment	SAF
Table 14.3.1.2.1	Treatment-Emergent Adverse Events by System Organ Class and Preferred Term for Initial-treatment	SAF
Table 14.3.1.2.2	Study Device Related Treatment-Emergent Adverse Events by System Organ Class and Preferred Term for Initial-treatment	SAF
Table 14.3.1.2.3	Study Procedure Related Treatment-Emergent Adverse Events by System Organ Class and Preferred Term for Initial-treatment	SAF
Table 14.3.1.2.4	Serious Treatment-Emergent Adverse Events by System Organ Class and Preferred Term for Initial-treatment	SAF
Table 14.3.1.2.5	Special Interest Treatment-Emergent Adverse Events by System Organ Class and Preferred Term for Initial-treatment	SAF
Table 14.3.1.2.6	Treatment-Emergent Adverse Device Effects by System Organ Class and Preferred Term for Initial-treatment for Initial-treatment	SAF
Table 14.3.1.2.7	Study Procedure Related Treatment-Emergent Adverse Device Effects by System Organ Class and Preferred Term for Initial-treatment	SAF
Table 14.3.1.2.8	Serious Treatment-Emergent Adverse Device Effects by System Organ Class and Preferred Term for Initial-treatment	SAF
Table 14.3.1.3.1.1	Treatment-Emergent Adverse Events by System Organ Class, Preferred Term, and Maximum Severity for Initial-treatment	SAF
Table 14.3.1.3.1.2	Treatment-Emergent Adverse Events by System Organ	SAF

This document is confidential.

Number	Title	Population
	Class, Preferred Term, and Severity for Initial-treatment	
Table 14.3.1.3.2	Study Device Related Treatment-Emergent Adverse Events by System Organ Class Preferred Term, and Maximum Severity for Initial-treatment	SAF

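### The overall adverse-event summaries for initial treatment and repeat-treatment give crude percentages over unequal follow-up (36 to about 92 weeks against 12), so they are not like for like for events that accrue over time

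*SAP*

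**What the plan says.** SAP 9.3 sets the statistic: "The number and percentage of subjects as well as number of events will be presented for the treatment-emergent AEs and ADEs summaries". For subjects injected again it adds: "TEAEs and TEADEs of the repeat-treatment subgroup from Week 36 or Week 48 or Visit 7c will be separately summarized". SAP 2.5 says that "applicable safety data will be analyzed by Group A, Group B, and repeat-treatment subgroup".

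The SAP's index of tables (Section 15) contains "Overall Summary of Treatment-Emergent Adverse Events for Initial-treatment" (Tables 14.3.1.1.1.1 and 14.3.1.1.1.2) and "Overall Summary of Treatment-Emergent Adverse Events for Repeat-Treatment" (Table 14.3.1.1.2).

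No table has a time denominator:
- SAP 9.1 measures exposure as volume and number of syringes.
- SAP 9.3 defines treatment-emergent as after dosing, with no end date and no cut at the repeat injection.
- Elapsed time since the initial application is derived for listings only.

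On follow-up, Protocol 10.11.13 says: "For subjects who are retreated at Week 36, the Week 48 Visit will be their end of study visit". It continues: "For subjects who are retreated at Week 48, the Week 60 Visit will be their end of study visit". A subject retreated at Visit 7c finishes at Visit 9c, 12 weeks later. Protocol 7.1 gives Visit 7c no visit window. The only limit is in Protocol 9.4: "Each subject is expected to be in the clinical investigation for a maximum of 104 weeks including the temporary hold on repeat-treatment".

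**The concern.** A crude percentage of subjects with an event rises with the length of observation. The initial-treatment summary covers at least three times the follow-up of the repeat-treatment summary. How much longer depends on how many subjects were caught by the hold, which is an operational matter unrelated to either device.

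Safety after repeat-treatment is a stated objective (SAP 2.4). The protocol's revision history records that follow-up after it was lengthened from one to three months at FDA request. A reader of the report will naturally set Table 14.3.1.1.2 beside Tables 14.3.1.1.1.x to ask whether a second exposure is tolerated as well as the first. SAP 9.3 splits only injection-site reaction AEs by device and pools the rest across devices. The pooled summaries therefore include unrelated background events, which are the ones most likely to accumulate with time.

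**Working it through.** **Follow-up lengths.** The plan's own visit weeks reproduce: 36 + 12 = 48 (Visit 9a) and 48 + 12 = 60 (Visit 9b). The repeat phase is therefore nominally 12 weeks on each route. The initial phase of a retreated completer is:
- 36 weeks if retreated at Visit 6;
- 48 weeks if retreated at Visit 7;
- at most 104 − 12 = 92 weeks if retreated at Visit 7c, or 90 if the 104 weeks include up to 14 days of screening.

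Ratios to the repeat phase: 36/12 = 3.0, 48/12 = 4.0, 92/12 = 7.7. The 36 and 92 weeks are derived, not stated, and assume that initial-phase events stop counting at the repeat injection. A subject not retreated at Visit 7c could have up to about 104 weeks. Early withdrawals may have fewer than 36.

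**Same constant rate in both phases.** The documents give no adverse-event rate, so the share of subjects with an event per 12 weeks, r, is an assumption shown as a range. The share with at least one event in w weeks is 1 − (1 − r)^(w/12).

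| r per 12 weeks | Repeat, 12 wk | Initial, 36 wk | Initial, 48 wk | Initial, 92 wk |
|---|---|---|---|---|
| 5% | 5% | 14.3% | 18.5% | 32.5% |
| 10% | 10% | 27.1% | 34.4% | 55.4% |
| 20% | 20% | 48.8% | 59.0% | 81.9% |

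Worked row: 1 − 0.9^3 = 27.1%; 1 − 0.9^4 = 34.4%; 1 − 0.9^7.67 = 55.4%. The underlying rate is identical in both phases: −ln(0.9)/12 × 52.18 × 100 = 45.8 per 100 subject-years.

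**Early events added.** Let a share a of subjects have an event soon after injection in each phase, on top of the steady rate: 1 − (1 − a)(1 − r)^(w/12). With a = 20% and r = 10%:
- repeat phase: 1 − 0.8 × 0.9 = 28.0%;
- initial phase: 1 − 0.8 × 0.729 = 41.7% at 36 weeks, 47.5% at 48 and 64.3% at 92.

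The ratio falls to between 41.7/28.0 = 1.5 and 64.3/28.0 = 2.3.

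**Early events only.** With r = 0 both phases show a, and window length has no effect.

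**No cut at the repeat injection.** If the initial-treatment tables run to the end of study, their windows become 48, 60 and up to 104 weeks. At r = 10% with no early component, the figures are 1 − 0.9^4 = 34.4%, 1 − 0.9^5 = 41.0% and 1 − 0.9^8.67 = 59.9%. The gap widens, and the same events can appear in both sets of tables.

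**The case against.** The strongest reply is that nobody plans this comparison. SAP 2.4 and 3.4 compare the devices after initial and touch-up treatment, and describe repeat-treatment for the investigational filler alone. Before retreatment, the two sides of one face have the same time at risk. The groups named in SAP 2.5 are side allocations and a subgroup of subjects, not two phases. All of this stands. The problem lies in how two descriptive summaries will be read, not in a planned test.

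The overlap is also narrow. The index has one repeat-treatment AE summary (Table 14.3.1.1.2) and one listing (Table 14.3.2.8). The AE and ADE tables by system organ class are all for initial treatment. A reader might infer a whole parallel set of mismatched tables, but the index does not show one.

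A reader might further infer that repeat-treatment must look safer by construction, by 2.7- to 5.5-fold. That needs a constant rate, which the documents do not support for device effects. Protocol 6.1 calls the common risks short-term. The comparator's instructions for use (Protocol 22.3) put onset of vascular occlusion with necrosis or vision abnormalities between immediate and one week. Diaries cover four weeks after every session, and SAP 9.4 tabulates visual findings by visit. Scheduled contact also thins after Week 12, with none between Week 48 and Visit 7c, so a constant observed rate out to 92 weeks is an upper illustration.

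These points limit the size and reach of the problem. They do not remove it for events that accrue over time, and none supplies the missing end to the initial-treatment window.

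**Conclusion.** The point holds in a limited form. The overall summaries in Tables 14.3.1.1.1.x and 14.3.1.1.2 are not like for like for events that accrue with time, and the SAP does not say where the initial-treatment window ends. The distortion ranges from none (all events early), through 28% against 42% to 64% (20% early plus 10% per 12 weeks), to 10% against 27% to 55% (10% per 12 weeks, constant). These rates are assumptions, and the durations are nominal values for retreated completers. The actual initial-phase percentage would mix 36, 48 and variable Visit 7c durations in proportions that the documents do not give.

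Diary injection-site reactions are largely unaffected, although the initial phase can include a touch-up session. The split-face device contrast before retreatment is also largely unaffected. No confirmatory conclusion depends on this point. It is a worthwhile improvement to descriptive safety reporting.

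**What to change.** In SAP 9.3:

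1. End the initial-treatment AE window at the repeat injection or, without one, at the last visit.
2. Add to the overall summaries a version with the same windows in both phases: onset within 28 days (the diary period) and within 84 days (the follow-up after repeat-treatment) of injection. State whether the initial-phase clock starts at the initial or the touch-up injection. Counted from the initial injection, 28 days reach only about 14 days past a Week 2 touch-up.
3. For the whole phases, add events per subject-time, with the subject-time shown.
4. Show TEAEs and TEADEs for all SAF subjects and for the retreated subjects. Do not compare SAEs or AESIs between phases within the retreated subjects. Protocol 9.2.2 and SAP 2.6.4 bar anyone with such an event after the initial or touch-up injection, so the initial-phase count there would be close to zero by eligibility and repeat-treatment would look worse. Show SAEs and AESIs for the full SAF, with a footnote on this selection.

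The cost is SAP wording and a few extra tables. Onset dates (Protocol 12.2) and application dates (Protocol 8.4.1) are already collected. The downside is that events after 84 days appear only in the whole-phase rates.
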